	Week 37	-	Day 85 to Day 91 of open-label period
	Week 38	-	Day 92 to Day 98 of open-label period
	Week 39	-	Day 99 to Day 105 of open-label period
	Week 40	281	Day 106 to Day 112 of open-label period
	Week 41	-	Day 113 to Day 119 of open-label period
	Week 42	-	Day 120 to Day 126 of open-label period
	Week 43	-	Day 127 to Day 133 of open-label period
	Week 44	-	Day 134 to Day 140 of open-label period
	Week 45	-	Day 141 to Day 147 of open-label period

	Week 46	-	Day 148 to Day 154 of open-label period
	Week 47	-	Day 155 to Day 161 of open-label period
	Week 48	-	Day 162 to Day 168 of open-label period
	Week 49	-	Day 169 to Day 175 of open-label period
	Week 50	-	Day 176 to Day 182 of open-label period
	Week 51	-	Day 183 to Day 189 of open-label period
	Week 52	365	Day 190 to Day 196 of open-label period
No further analysis visit			

Assessment window for the assessments performed at study visit (e.g. DLQI, [REDACTED], safety assessment except AEs etc.) until Week 52

When the assessments are summarized by visit, they are based on the visit numbers as recorded in eDiary or eCRF except for end of treatment (ETD) visit, and study discontinuation (SD) visit. **ETD visit, SD visit** will be remapped to the scheduled visit. Safety follow-up visit or unscheduled visits will NOT be remapped (except for the unscheduled visit to be considered as baseline).

The assessment window is based on the study assessment schedule. For participants initially randomized to placebo and switched to LOU064, the date of first OL study treatment will be considered. The assessments under placebo treatment will not be remapped to the visits during OL period and the assessments under LOU064 treatment will not be remapped to the visits during DB period.

The protocol defined assessment schedule is shown in [Table 2-6](#). For ECG, at Week 2, 12, 52 and SD visit pre and post-dose assessments will be collected. ETD visit can be remapped to Week 24 only, and SD visit can be remapped to Week 2, 12 and 52.

Table 2-6 Assessment schedule

Visit Name	BSL	week 2	week 4	week 8	week 12	week 16	week 20	week 24	week 32	week 40	week 52	ETD	SD
Scheduled visit Day	1	15	29	57	85	113	141	169	225	281	365	-	-
Vital Signs													
Clinical Chemistry*	X	X	X	X	X	X	X	X	X	X	X	X	X
Hematology													
Urinalysis													
Coagulation Panel	X		X		X			X		X	X	X	X
Weight					X						X	X	X
ECG	X	X ²			X ²			X			X ²	X	X ²
DLQI	X		X		X			X			X	X	X

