X: to be recorded, BSL: baseline, ETD: early treatment discontinuation, SD: study discontinuation

¹ only post-baseline assessments² pre and post dose

* C-reactive protein (CRP), estimated Glomerular Filtration Rate (eGFR): assessed at screening, baseline, weeks 12, 24 and 52. Fasting glucose assessed at baseline, weeks 2, 12 and 52.

Table 2-7 shows the assessment windows for the assessments collected at every visit (i.e., Vital signs, Clinical Chemistry, Hematology, Urinalysis).

If more than one assessment fall into the interval,

- Then if there is the scheduled visit recorded in eDiary or eCRF, this visit will be chosen.
- If no, the earliest visit day will be chosen.

For example, when a participant discontinued study treatment after completing Week 2 and Week 4, and ETD visit occurred on Day 35 and SD visit occurred on Day 80, the ETD visit will be mapped to Week 8 and SD visit will be remapped to Week 12.

If a participant visited the site earlier than scheduled visit day, e.g., Week 4 on Day 25, ETD visit on Day 29, ETD visit will be remapped to Week 4. As the participant already performed Week 4 scheduled visit, the remapped Week 4 (ETD visit) will not be used.

If a participant visited the site late than scheduled visit day, e.g., Week 4 on Day 25, ETD visit on Day 58, SD visit on Day 85, both ETD visit and SD visit will be remapped to Week 12. In this case, ETD visit will be used as Week 12, and Week 8 will be missing.

Table 2-7 Assessment window for vital signs, clinical chemistry, hematology, urinalysis until Week 52

Assessment visit	Scheduled Visit Day	Assessment Window
Week 2	15	Day 2 to Day 15
Week 4	29	Day 16 to Day 29
Week 8	57	Day 30 to Day 57
Week 12	85	Day 58 to Day 85
Week 16	113	Day 86 to Day 113
Week 20	141	Day 114 to Day 141
Week 24	169	Day 142 to Day 169
Week 32	225	Day 170 to Day 225
Week 40	281	Day 226 to Day 281
Week 52	365	Day 282 to Day 365

For the assessments which are not collected at every visit (e.g., DLQI), assessment window will be combined. For example, DLQI is collected at Week 4, Week 12, Week 24 and Week 52. The assessment window will be combined as follows:

Table 2-8 Assessment window for DLQI until Week 52

Assessment visit	Scheduled Visit Day	Assessment Window
Week 4	29	Day 2 to Day 29
Week 12	85	Day 30 to Day 85
Week 24	169	Day 86 to Day 169
Week 52	365	Day 170 to Day 365

Table 2-9 shows the assessment windows of days for each assessment.

Table 2-9 Assessment windows by assessment

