2.5.1.3 Handling of intercurrent events

Participants who discontinue from study treatment early due to any reason will be encouraged to stay in the study following the procedures. Every effort will be made to continue to follow participants who discontinued from study treatment up to Week 12. These are considered as Retrieved drop out (RDO) participants.

The analysis will account for different intercurrent events as explained in the following:

1. Discontinuation of study treatment prior to Week 12 due to any reason:

A treatment policy strategy will be applied and these intercurrent events will be ignored. Data collection will be maintained and available measurements post-treatment discontinuation will be used as if they had been obtained under the treatment assigned at randomization. i.e, RDO data collected after study treatment discontinuation will be used for analysis. In case of missing values, a multiple imputation approach will be applied (see [Section 2.5.1.4](#) for details).

2. Intake of rescue medication as per protocol, or switch of background medication, or intake of other prohibited medication (except for strongly confounding prohibited medication listed below), or participants non-compliant (dose interruption) to treatment prior to Week 12:

A treatment policy strategy will be applied in the same way as described above. Data collected after these events will be used for analysis.

3. Intake of strongly confounding prohibited medication:

- Biologics treatment at any time before Week 12 (as identified by PD M-COMD03)
- Cyclosporin after Week 8 to Week 12 (as identified by PD M-COMD04)
- Systemic corticosteroids after Week 8 to Week 12 (as identified by PD M-COMD04)

A composite strategy will be applied. Measurements after this event will be excluded from the analysis and will be imputed using the worst value of the endpoint (i.e., 42 for UAS7).

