UAS7 \leq 6 at Week 12	Odds ratio between treatment groups	A treatment policy strategy: RDO data or data collected after the IE will be used. In case of missing values of RDO data, derivation based on the multiply imputed UAS7 described in Section 2.5.1.3 will be applied.
		A composite strategy: UAS7 response after the intercurrent event will be excluded and UAS7 \leq 6 will be derived from imputed UAS7 score using the worst value (i.e., 42).
UAS7 = 0 at Week 12	Odds ratio between treatment groups	Same as UAS7 \leq 6 at Week 12.
ISS7 score change from baseline to Week 12	Mean difference between treatment groups	Same as the primary estimand, see Section 2.5.1.3
HSS7 score change from baseline to Week 12	Mean difference between treatment groups	Same as the primary estimand, see Section 2.5.1.3
UAS7 \leq 6 at Week 2	Odds ratio between treatment groups	Same as UAS7 \leq 6 at Week 12.

Endpoint	Summary measurement	Handing of intercurrent event
		Note: As this endpoint is for the score at W2, some intercurrent events, e.g. intake of strongly confounding prohibited medication, will not be considered.
DLQI 0/1 at Week 12	Odds ratio between treatment groups	Same as UAS7 \leq 6 at Week 12. In case of missing values of RDO data, derivation based on the multiply imputed DLQI score with same approach as UAS7 will be applied.
Cumulative number of weeks with an UAS7 \leq 6 response between baseline and Week 12	Ratio of response rate between treatment groups	Same as UAS7 \leq 6 at Week 12. Derivation based on the multiply imputed UAS7 described in Section 2.5.1.3 will be applied.
Cumulative number of weeks with an AAS7=0 response between baseline and Week 12	Ratio of response rate between treatment groups	Same as UAS7 \leq 6 at Week 12. Derivation based on the multiply imputed AAS7 with same approach as UAS7 will be applied.

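### The only rule in the SAP for choosing a Week 12 DLQI record can let an early treatment-discontinuation value stand as Week 12 data, which the treatment-policy handling of DLQI 0-1 does not call for

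*SAP*

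**What the plan says.** **Visit mapping (SAP 2.1.1.5).** DLQI is named in the heading of the study-visit rules: "Assessment window for the assessments performed at study visit (e.g. DLQI". The text that follows is introduced for assessments summarised by visit. ETD and SD visits are remapped to scheduled visits, whereas "Safety follow-up visit or unscheduled visits will NOT be remapped", apart from an unscheduled visit that serves as baseline. For DLQI the windows are merged: "DLQI is collected at Week 4, Week 12, Week 24 and Week 52. The assessment window will be combined as follows". Tables 2-8 and 2-9 both give Day 30-85 for Week 12.

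**Tie-break.** This is printed with Table 2-7, which covers vital signs, chemistry, hematology and urinalysis. A recorded scheduled visit is preferred; failing that, "If no, the earliest visit day will be chosen". In one worked example (ETD Day 58, SD Day 85): "In this case, ETD visit will be used as Week 12, and Week 8 will be missing".

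**Estimand handling.** Table 2-12 treats DLQI 0/1 in the same way as UAS7 ≤ 6. Retrieved drop-out (RDO) data, or data collected after the intercurrent event, are used under treatment policy, and "In case of missing values of RDO data, derivation based on the multiply imputed DLQI score with same approach as UAS7 will be applied". SAP 2.5.1.3 describes the RDO data thus: "RDO data collected after study treatment discontinuation will be used for analysis".

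**Visits after stopping (protocol 9.1.1).** The ETD visit takes place when treatment stops. Participants who stop before Week 12 are asked to return up to Week 12, where an SD visit is done (that sentence is partly redacted). Those who decline go to the safety follow-up visit, for which Table 8-1 schedules no DLQI.

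**The concern.** DLQI asks about the previous 7 days (protocol 8.3.2.1), so a value taken at the ETD visit mostly describes life on treatment. Placed in the Week 12 cell, it makes that cell look observed. The imputation in 2.5.1.4 is then not triggered and, in some visit patterns, a later retrieved value is discarded. UAS7 has no such problem: a discontinuer's Week 12 score comes from diary Days 78-84 (SAP Table 2-4).

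DLQI 0-1 at Week 12 is alpha-controlled. It is H07 in the UAS7 scenario and H06 in the ISS7/HSS7 scenario, and in each the two cumulative-weeks hypotheses come after it in a strict hierarchy. Two programmers could follow the SAP and build different responder data. SAP 2.5.2.5 plans no sensitivity analysis for secondary endpoints, so the difference would not show.

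**Working it through.** **1. The SAP's own examples.** Applying the Table 2-7 windows and tie-break reproduces all three. ETD Day 35 with SD Day 80 gives Week 8 and Week 12 ("ETD visit occurred on Day 35 and SD visit occurred on Day 80, the ETD visit will be mapped to Week 8"). ETD Day 29 after a Week 4 visit on Day 25 is not used. ETD Day 58 with SD Day 85 gives the ETD as Week 12.

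**2. The same logic in the DLQI window (Day 30-85).**

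| Visits | Week 12 DLQI under the mapping | Tie-break needed? | Under Table 2-12 and 2.5.1.3-2.5.1.4 |
|---|---|---|---|
| ETD Day 30, follow-up declined | ETD Day 30 | No | Missing, imputed |
| ETD Day 30, SD Day 88 | ETD Day 30 (SD goes to Week 24) | No | Retrieved SD value |
| ETD Day 35, SD Day 80 | ETD Day 35 | Yes | Retrieved SD value |
| ETD Day 58, SD Day 85 | ETD Day 58 | Yes | Retrieved SD value |
| ETD Day 30, scheduled Week 12 recorded on Day 85 | Scheduled visit | Settled by scheduled-first | Scheduled visit |
| ETD Day 20, SD Day 85 | SD Day 85 (ETD goes to Week 4) | No | Retrieved SD value |

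The largest gap is 85 − 30 = 55 days, or 7.9 weeks. The first row rests on visible text alone. The other rows with an SD visit depend on how the Week 12 visit of a discontinuer is labelled.

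**3. Size.** The documents give no rate of stopping treatment and no DLQI response rates, so what follows is assumption.

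- Inputs: 300 and 150 randomized, and about 10% drop-out at Week 12 (SAP 3.1), used as a proxy for stopping treatment before Week 12.
- Share of stops with an ETD on Day 30-84, if stopping is even over Days 1-84: 55/84 = 0.655.
- Exposed share of each arm: 0.10 × 0.655 = 6.5%, which is 19.6 of 300 and 9.8 of 150. This counts everyone with an ETD in the window and no recorded scheduled Week 12 visit, so it is an upper figure for this scenario.
- Shift in an arm's rate per 10-point difference between ETD and true Week 12 response: 0.0655 × 10 = 0.65 points. A 30-point difference gives 0.0655 × 30 = 2.0 points.
- Other stopping rates, even timing: 5% gives 3.3% and 15% gives 9.8%.
- Other timing at 10%: front-loaded (weight 85 − d) 1540/3570 = 0.431, so 4.3%; back-loaded (weight d) 3135/3570 = 0.878, so 8.8%.
- Both varied together: 0.05 × 0.431 = 2.2% to 0.15 × 0.878 = 13.2%.
- Declined follow-up only, if 25-75% decline (10%, even timing): 0.0655 × 0.25 = 1.6% to 0.0655 × 0.75 = 4.9%, about 5-15 of 300 and 2-7 of 150.

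**The case against.** The best reply is scope. The mapping is introduced for by-visit summaries, and the laboratory, ECG and vital-sign sections call on the remapping only for by-visit tables. The DLQI test is described in 2.5.2.1-2.5.2.4, which point to 2.1.1.5 only for the AAS7 diary score. Read that way, ETD values never enter the tested data. This stands as a possible reading, and it is why the point is conditional. It does not close the gap, because those sections do not say which DLQI record is Week 12 for someone who stopped early.

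A second reply is that the steps run in sequence: 2.1.1.5 fills the visit and 2.5.1.4 imputes whatever is still missing. That is coherent, but it lets a value taken at discontinuation stand where the treatment-policy text asks for data after it.

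Third, the tie-break and worked examples belong to Table 2-7. That is correct. A reader might infer that the SAP expressly prefers an early ETD over a later SD for DLQI; it does so only if the tie-break is carried over. A recorded scheduled Week 12 visit would win in any case, and the redaction in protocol 9.1.1 hides how often one exists.

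Fourth, the SAP never classifies ETD values, so calling them not RDO data is an inference. It is a reasonable one, given the timing of the visit and the 7-day recall.

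**Conclusion.** The concern holds in a limited form. The SAP's one Week 12 record rule for DLQI, if used for the test, departs from the treatment-policy handling for participants who stop treatment with an ETD on Day 30-84 and have no recorded scheduled Week 12 visit. The clearest case is declined follow-up, which needs neither the tie-break nor the redacted text.

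The effect is probably small: about 6.5% of each arm exposed and 0.65 points in an arm's rate per 10-point response difference, on the proxy and timing assumptions above. Similar shifts in both arms would largely cancel in the risk difference; opposite shifts would add. It could matter for a borderline DLQI test, hardly for a clear one.

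Three stronger inferences are not supported:

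- **That the rule favours remibrutinib.** The direction depends on why people stop, and protocol 6.1.4 gives both adverse events and loss of efficacy as examples.
- **That remapped ETD values would make the 50% RDO check pass wrongly.** SAP 2.5.1.3 describes RDO data as collected after discontinuation, and no separate DLQI check is set out.
- **That the main results are exposed.** The primary, co-primary and other eDiary endpoints use diary windows and are unaffected, as are completers.

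**What to change.** In SAP 2.1.1.5 or 2.5.2.1, state that for the Week 12 DLQI 0-1 analysis in participants who stopped treatment before Week 12 the record is, in order:

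1. the recorded scheduled Week 12 visit;
2. otherwise the SD visit closest to Day 85, within a window that the sponsor sets in advance and that extends past Day 85 (such a visit is not also mapped to Week 24);
3. otherwise Week 12 is missing and is imputed under 2.5.1.4.

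Add that a remapped ETD value does not fill Week 12 in this analysis and is not RDO data. The mapping for by-visit summaries can stay as it is.

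SAP 2.13 confines formal testing to the primary analysis, and amendment 5 is dated before the final analysis only, so testing may already have been done. If so, keep that result as the confirmatory one and report the re-derived DLQI 0-1 result as a labelled sensitivity analysis.

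The cost is a few lines of SAP text, a small programming change and slightly more imputed DLQI values, plus one extra output if testing is complete. No new data are needed.

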Participants should be seen for all visits/assessments as outlined in the assessment schedule ([Table 8-1](#)) or as close to the designated day/time as possible. Missed or rescheduled visits should not lead to automatic discontinuation.

For participants who discontinue from study treatment refer to [Section 9.1.1](#).

Participants who discontinue from the study or withdraw their consent/oppose the use of their data/biological samples should be scheduled for a final evaluation visit, if they agree, as soon as possible, at which time all of the assessments listed for the final visit will be performed. At this final visit, all dispensed investigational product should be reconciled, and the adverse event and concomitant medications not previously reported must be recorded on the CRF.

The "X" in the table denotes the assessments to be recorded in the clinical database or received electronically from a vendor. The "S" in the table denotes the assessments that are only in the participant's source documentation and do not need to be recorded in the clinical database.

As per [Section 4.6](#), during a Public Health emergency as declared by Local or Regional authorities i.e., pandemic, epidemic or natural disaster that limits or prevents on-site study visits, alternative methods of providing continuing care may be implemented by the investigator as the situation dictates. If allowed by local Health Authority and depending on operational capabilities, phone calls, virtual contacts (e.g., tele consult) or visits by site staff/ home nursing staff to the participant's home, can replace on-site study visits, for the duration of the disruption until it is safe for the participant to visit the site again.

[REDACTED]

The preferred sequence of assessments during study visits is PRO completion, ECG collection, followed by vital signs, and blood sampling.

[figure not shown]
[figure not shown]
[figure not shown]

Table 8-1 Assessment Schedule

Period	Screening	Treatment											Follow-up	Unscheduled visit	
Visit Name	Screening	Baseline/ Randomization ¹	week 2 ¹	week 4	week 8	week 12 ¹	week 16	week 20	week 24	week 32	week 40	Early treatment discontinuation	week 52/Study discontinuation ¹	week 56/Safety FU/Study completion	Unscheduled visit
Days	-28 to -1	1	15	29	57	85	113	141	169	225	281		365	394	-
Informed consent	X														
IRT transaction	X	X		X	X	X	X	X	X	X	X	X	X	X	
Inclusion / Exclusion criteria	X	X													
Randomization		X													

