For participants who discontinue from study treatment prior to week 12, where possible they should be requested to return for visits after the Early treatment discontinuation visit as per the Assessment Schedule ([Table 8-1](#)) up to and including the week 12 timepoint. At the week 12 timepoint the study discontinuation visit should be performed [REDACTED]. If the participant declines to continue with assessments as per the visit schedule up to week 12, then they should complete the safety follow-up visit after the Early treatment discontinuation visit.

Participants who discontinue from study treatment after week 12 should complete the safety follow-up visit indicated in the Assessment Schedule ([Table 8-1](#)) whenever possible.

If the participant cannot or is unwilling to attend any visit(s), the site staff should maintain regular telephone contact with the participant, or with a person pre-designated by the participant. This telephone contact should preferably be done according to the study visit schedule.

After discontinuation from study treatment, at a minimum, in abbreviated visits, the following data should be collected at clinic visits or via telephone/email contact:

- New / concomitant treatments
- Adverse Events / Serious Adverse Events

The investigator must also contact the IRT to register the participant's discontinuation from study treatment.

If discontinuation occurs because treatment code has been broken, please refer to Emergency breaking of treatment code section.

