2.5.1.4 Handling of missing values

Missing data imputation will be performed for the analyses when using statistical model.

Handling of missing RDO data

If no RDO data was collected after study treatment permanent discontinuation, missing data will be imputed based on the following rules:

- For participants in the active treatment arms, if sufficient RDO data, missing data will be imputed using MI based on observed RDO data in the corresponding active arm. If not feasible (e.g., very limited RDO data), missing data will be imputed based on observed data in the placebo arm under the assumption of jump to reference (J2R) using MI.
- For participants in the placebo arm, if sufficient RDO data, missing data will be imputed using MI based on observed RDO placebo arm data. If not feasible (e.g., very limited RDO data), missing data will be imputed using MI under the MAR assumption based on the observed placebo arm data.

Handling of other missing data

If there is any missing data prior to Week 12, the missing data will be handled following the MAR assumption.

The detailed steps for handling of the intercurrent events and analyses are described below.

Step 1: Identify the participants with intercurrent events.

Step 2: For participants with intercurrent event 1 (Discontinuation of study treatment prior to Week 12 due to any reasons), determine the imputation strategy based on the amount of RDO data.

- Calculate the percentage of RDO data available at Week 12 in participants with intercurrent event 1 by treatment group
- If $\geq 50\%$ of participants had RDO data at Week 12, consider RDO data is sufficient
- If $< 50\%$ of participants had RDO data at Week 12, consider RDO data is not sufficient

Step 3: Perform the missing data imputation.

- For participants with intercurrent event 3 (Intake of strongly confounding prohibited medication), set missing at all visits after the event
- Perform the missing data imputation under MI framework according to the imputation strategy on Step 2. At the same time, missing data imputation of other missing data (i.e., non RDO data) will also be performed. The details on MI are described in [Section 5.4.3](#)

- Replace the values at all visits after the intercurrent event 3 with the worst value

Step 4: Perform the analysis.

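### The DLQI Week 12 remapping window closes on the target day, so an early discontinuer's Week 12 value collected on Day 86 or later is filed under Week 24

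*SAP*

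**What the plan says.** For assessments made at study visits, SAP 2.1.1.5 keeps the recorded visit number, with two exceptions: ETD and SD visits "will be remapped to the scheduled visit" according to study day. Table 2-8 gives the DLQI windows. Week 12 (scheduled Day 85) is "Day 30 to Day 85" and Week 24 (scheduled Day 169) is "Day 86 to Day 169". Table 2-9 repeats these limits. Table 2-7, for vital signs, chemistry, hematology and urinalysis, follows the same pattern: Week 12 is "Day 58 to Day 85" and Week 16 is "Day 86 to Day 113". If several records share a window, a recorded scheduled visit is used; failing that, the earliest record is used.

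Protocol 9.1.1 asks participants who stop treatment before Week 12 to keep attending through Week 12, and adds: "At the week 12 timepoint the study discontinuation visit should be performed". Part of that sentence is redacted. Protocol section 8 asks that visits be made on the planned day or "as close to the designated day/time as possible", and no visit tolerance appears in the visible text.

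DLQI 0-1 at Week 12 is a formally tested secondary endpoint (H07 in the UAS7 scenario, H06 in the ISS7/HSS7 scenario). SAP Table 2-12 handles treatment discontinuation for it by treatment policy: retrieved drop-out (RDO) data are used, and missing values are multiply imputed in the same way as for UAS7.

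**The concern.** The window has no room after its target day. For participants who stop early and return at Week 12, the return is an SD visit, so the study-day rule decides where the value goes. One day of lateness moves an observed Week 12 DLQI value 12 weeks forward. A participant still on treatment who attends equally late is not affected, because that visit keeps its recorded number. The rule therefore acts only on discontinuers, whose retrieved data the treatment-policy strategy is meant to use.

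Two things are at stake. At Week 12, a tested endpoint may use an imputed or older value where a current one was observed. At Week 24, a value taken at about 12 weeks, from someone not asked to attend efficacy visits beyond that, is presented as Week 24 data.

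**Working it through.** **Reproducing the SAP's own examples.** Looking up study days in Table 2-7 gives ETD Day 35 → Week 8 and SD Day 80 → Week 12; ETD Day 29 → Week 4; ETD Day 58 and SD Day 85 → both Week 12, with the ETD record used. All five assignments agree with the SAP's text. The third example also shows that an on-time SD visit already gives way to an earlier ETD visit in the same window.

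**Moving the SD visit by one day.** On Day 84 or 85, DLQI goes to Week 12. On Day 86 it goes to Week 24.

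**Adding the earliest-record rule.** With only ETD and SD visits available, the source of the Week 12 DLQI value is:

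| ETD visit | SD on Day 85 | SD on Day 86 |
|---|---|---|
| Day 2-29, or not done | SD value | none, so imputed |
| Day 30-84 | ETD value | ETD value |

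Lateness alone empties Week 12 only in the first row. In both rows a Day 86 SD value is labelled Week 24.

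**Size.** The documents give neither the spread of visit days nor the number of early discontinuers who return, so these inputs are assumptions:

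- Share of SD visits on Day 86 or later, if symmetric around Day 85: uniform ±3, ±5, ±7 days gives 3/7, 5/11, 7/15 = 0.43, 0.45, 0.47; a normal distribution with standard deviation 3, 5 or 7 days gives 0.43, 0.46, 0.47.
- Early discontinuers: 10% × 450 = 45, borrowing the drop-out rate in protocol 12.8.1.
- Returning for the Week 12 SD visit: 60% to 90%, i.e. 45 × 0.60 = 27 to 45 × 0.90 ≈ 40.
- Values labelled Week 24: 27 × 0.43 ≈ 12 to 40 × 0.47 ≈ 19.
- ETD day uniform over Day 2-84 and unrelated to lateness: 28 of 83 days fall on Day 2-29, so 28/83 = 0.34.
- Week 12 value lost through lateness alone: 12 × 0.34 ≈ 4 to 19 × 0.34 ≈ 6, both arms together.

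**Laboratory and vital signs.** Safety summaries stop at last dose plus 28 days (SAP 2.1.1.4 and 2.7). A Day 86 SD visit counts only if the last dose was on Day 58 or later (58 + 28 = 86). That participant's ETD visit, due when treatment stops, then falls in Day 58-85 and supplies Week 12. With an earlier last dose, the Day 86 visit is outside the summaries anyway.

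**ECG.** Day 86 falls in the Week 24 window of Table 2-9, but SAP 2.1.1.5 lets SD ECGs be remapped only to Weeks 2, 12 and 52. The SAP does not say what happens.

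**The case against.** The strongest reply is that the table lookup is correct but matters little. Most of this reply stands, and it limits the size of the point:

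- A reader might take all 12 to 19 late values as lost Week 12 values. They are not: where ETD falls on Day 30-84, Week 12 is filled from ETD whether or not the SD visit is late.
- A reader might infer that the rule under which at least 50% "of participants had RDO data at Week 12, consider RDO data is sufficient" could be met only if 88% to 94% of discontinuers return (0.5/0.57 to 0.5/0.53). That counts only on-time SD visits and ignores ETD values that also map to Week 12. SAP 2.5.1.4 sets the rule in the UAS7 section and does not say whether it is recalculated for DLQI. A switch to jump-to-reference is therefore possible but not shown.
- A reader might extend the problem to laboratory and vital-sign data. The on-treatment limit leaves almost nothing there unless the ETD visit was missed.
- Calling the late SD ECG lost goes beyond the text; the case is unresolved.
- The 10% in protocol 12.8.1 reduces 300/150 to 270/135 evaluable participants. It is not a forecast of discontinuers who return, so 45 is a stand-in.
- Remapping may not be the only route. A visit recorded as Week 12 rather than SD would keep its number and take precedence, and the redaction in protocol 9.1.1 leaves open how sites record it.

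None of this supplies another rule for an SD visit on Day 86. As written, its DLQI value goes to Week 24.

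**Conclusion.** The point holds for DLQI. The SAP's stated rule mislabels Week 12 retrieved values from early discontinuers seen after Day 85, and treats them differently from equally late on-treatment participants. About 4 to 6 participants would lose an observed Week 12 value through lateness alone, and about 12 to 19 values would be shown as Week 24. These counts rest on 45 discontinuers, 60-90% returning, 43-47% of SD visits late, and ETD days spread evenly over Day 2-84, none of which the documents establish.

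UAS7, ISS7, HSS7 and AAS7 use eDiary day windows, so the documents do not support any inference that the primary or co-primary result is at risk. The point deserves correction because it concerns observed data for an alpha-controlled endpoint and costs little to repair.

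**What to change.** Add to SAP 2.1.1.5: for participants who stop study treatment before Week 12, the SD visit made at the Week 12 timepoint under protocol 9.1.1 is assigned to Week 12 for DLQI if it occurs up to Day 99 (the midpoint of Day 85 and Day 113); it is not remapped to Week 24; and it takes precedence over an ETD value in the same window. Leave the other windows unchanged. Without the precedence clause, the earliest-record rule would still discard the SD value whenever ETD fell on Day 30-84. In the same edit, state how an SD ECG after Day 85 is handled.

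The last SAP amendment is logged as prior to the final analysis, whereas those before it are logged as prior to the primary analysis, so the DLQI test may already have been run. If so, report the number of displaced values by arm and a re-analysis with the corrected mapping.

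The cost is a few lines of SAP text and a small change to the mapping program, with no new data. The downside is that a few values up to 14 days late count as Week 12; late on-treatment visits are already accepted in this way.
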